3.2.4 Oral Glucose Tolerance Test (OGTT)

For the OGTT patients will be admitted to the CTRU in the a.m. after at least 8 hours of fasting. An IV will be put in place for blood draws. Patient will be asked to drink 75 grams of glucola after drawing time 0' sample of OGTT. Samples for blood glucose levels by glucose oxidase method and insulin levels and C-peptide by immulite will be measured at -5, 0, 10, 20, 30, 60 and 120 min. Insulin secretion and sensitivity will be calculated from the OGTT glucose, insulin and C-peptide levels using the homeostasis model assessment (HOMA), quantitative insulin sensitivity check index (QUICKI) and modeling of insulin secretion. Blood samples will be saved and sent to the Core Lab for Clinical Studies for measuring of peripheral immune function.

Protocol

Version 6: August 25, 2020

3.2.5 Hemoglobin A1c testing

Approximately 2 tsp of blood will be drawn from your arm to conduct blood tests that include blood glucose levels and hemoglobin A1c

3.2.6 Cognitive testing.

Participants will be assessed for cognitive function using well-validated computer-based tests available from the NIH Toolbox²⁷. Episodic memory²⁸, executive function, and processing speed²⁹ test scores are expected to be lower in obese relative to non-obese individuals. The testing should take approximately 30 min.

3.2.7. Study Visit

3.2.7.1 Anticipated duration of entire research activity per patient

Participant involvement will last for approximately 6 hours over the span of 1-3 days including phone screening and electronic survey completion. If there is a technical problem with the MR data collection, participants may be asked to repeat the MR session. In this case, total participation would last up to 8 hours. Participants will be provided with lunch after the OGTT.

3.3. Statistical Analysis:

Aim 1: To determine if obesity is associated with increased cellularity and glial levels in the brain using MR-based Diffusion Basis Spectrum Imaging (DBSI) and qGRE (GEPCI/SMART). We will use analyses of covariance (ANCOVA) to compare MRI-based metrics between obese and non-obese controlling for age, sex, gender, and insulin resistance .
Aim 2: To determine if indicators of neuroinflammation, including cellularity and glial levels are associated with cognitive performance in obesity. We will use Pearson's *r* correlational analyses to determine whether MRI metrics relate to impaired cognition in obesity.

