1.0 BACKGROUND AND RATIONALE

More than a third of individuals in the United States are obese³. Obesity has recently been associated with increased risk for cognitive impairment and dementia such as Alzheimer's disease (AD)⁴⁻¹⁰. In young and middle-aged people, higher BMI relates to diminished learning, memory, and executive function¹¹⁻¹⁴. Cournot et al. found that higher BMI during middle age is associated with impaired delayed recall at baseline and at several years follow-up¹¹. Long-term obesity (from age 25 through late midlife, mean age = 61 yrs) predicts lower Mini-Mental State Examination (MMSE) scores and impairments in memory and executive function in late midlife independent of age and education, according to the Whitehall II Cohort Study¹⁵. Although previous human studies have investigated structural and functional differences between obese and non-obese individuals, strong relationships between these differences and cognitive performance have not been found¹⁶. It is likely that a key specific component to obesity-related brain effects on cognition has yet to be studied.

Obesity is a disease characterized by chronic low-grade systemic inflammation¹⁷. We propose that **neuroinflammation** is a major mechanism by which young and mid-life overweight or obesity contributes to cognitive impairment. Reduced blood brain barrier integrity induced by chronic high fat diet is thought to be a major way in which pro-inflammatory elements cross over into the brain and induce neuroinflammation¹⁸. Indeed, recent studies in rodents show that diet-induced obesity induces neuroinflammation¹⁹⁻²³ accompanied by cognitive impairment^{19,23}. However, only a few studies have addressed these questions in obese humans^{22,24}.

The current proposal investigates whether indicators of neuroinflammation are present in **obese humans** and whether these indicators are associated with cognitive performance. We will use MR-based DBSI, an extension of diffusion weighted imaging (DWI) developed at Washington University School of Medicine (WUSM) by [name] that differentiates between axon/myelin integrity, axonal density, and extra-fiber components including inflammation and edema in white matter²⁵. In addition, we will use a complimentary MR-based multimodal approach that includes functional connectivity MRI (fcMRI) and quantitative gradient recalled echo (qGRE, GEPCI, SMART), which distinguishes neuronal, synaptic and glial components of the MR signal²⁶.

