2.0 OBJECTIVES

The objective of this proposal is to use MRI imaging to identify indicators of neuroinflammation in obese individuals. Further, greater neuroinflammation should correlate with greater cognitive impairment in obese individuals.

Aim 1: To determine if obesity is associated with increased cellularity and glial levels in the brain using MR-based Diffusion Basis Spectrum Imaging (DBSI) and qGRE (GEPCI/SMART).
Aim 2: To determine if indicators of neuroinflammation, including cellularity and glial levels are associated with cognitive performance in obesity.

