3.0 METHODS

3.1.1 Research Subjects:

We will study 10 non-obese and 10 obese adults, both male and female, who are non-diabetic, aged 18-75 years.

Protocol

Version 6: August 25, 2020

Inclusion criteria: Non-obese (18-25 kg/m²) or obese (BMI \geq 30 kg/m²), male or female, any race or ethnicity, aged 18-75 years.

Exclusion criteria: Exclusion criteria include the following: history of diabetes, >350 lb (scanner weight limit), binge eating disorder, history of or current serious neurological illness, current mental illness, not a native speaker of English, history of drug abuse or currently taking psychotropic medication, MRI contraindications. Additionally, participants will be excluded if they are currently pregnant (positive urine pregnancy test) or breastfeeding. Finally, any participant with tobacco use in the past month will also be excluded.

Sample size justification: We received funding to study 20 individuals. This is a pilot and feasibility study.

3.1.2. Recruitment:

We will call or email previous participants from a previous study of obesity (IRB#201104109; PI: [name]). Subjects will be screened on a private line in a private suite using the phone script. They will be informed of the nature of the experiment and, if interested, will be questioned about inclusion and exclusion criteria. Those subjects meeting these criteria, and expressing further interest after this screening will be scheduled for study visits.

We will also recruit through Volunteers for Health and make use of their services including Facebook, Centerwatch, and Twitter posts, and flyers (for email blasts and posting at various sites).

Upon arrival into the laboratory for the first session, if the investigators are satisfied that the subject meets all of the inclusion and exclusion criteria, and the subject agrees to participate, the Human Research Protection Office (HRPO) approved informed consent will be signed.

3.2. Experimental Design:

3.2.1. Facilities.

The MRIs will take place in a Siemens 3T scanner in the Center for Clinical Imaging Research (CCIR) at Barnes-Jewish Hospital or in the East Building at WUSM. Screening and cognitive testing will take place in a private testing room. Oral glucose tolerance tests (OGTTs) will take place at the Clinical Research Unit (CTRU) at WUSM.

3.2.2. Overview of Procedures.

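### Aim 2 correlates MRI metrics with cognition without adjusting for age in adults eligible from 18 to 75, although Aim 1 adjusts the same metrics for age, so the correlation can be biased by age

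*Combined protocol and SAP*

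**What the plan says.** Section 3.3 treats the two aims differently. For Aim 1 the MRI metrics are compared between obese and non-obese groups by ANCOVA, "controlling for age, sex, gender, and insulin resistance". For Aim 2 the same cellularity and glial measures are related to cognition by Pearson "correlational analyses to determine whether MRI metrics relate to impaired cognition in obesity". No covariate, partial correlation or regression is named, and no other section adds one.

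The rest of the plan bears on this as follows:

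- **Age range.** Section 3.1.1 enrols 10 obese and 10 non-obese adults "who are non-diabetic, aged 18-75 years", with no age matching or stratification.
- **Cognitive outcome.** Section 3.2.6 uses "well-validated computer-based tests available from the NIH Toolbox" and says that "test scores are expected to be lower in obese relative to non-obese individuals". It commits to neither age-corrected nor uncorrected scores.
- **Predicted direction.** Section 2.0 expects that "greater neuroinflammation should correlate with greater cognitive impairment in obese individuals".
- **Background.** Section 1.0 reports a cohort finding of "impairments in memory and executive function in late midlife independent of age and education".
- **Status.** Section 3.1.1 says of the sample size: "This is a pilot and feasibility study". No significance level or decision rule is given.

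**The concern.** Aim 1 already treats age as a variable that can distort these metrics. Aim 2 uses the same metrics without that control, in a sample that may span 57 years of age. If cognitive scores fall with age, which is an assumption here, there are two cases:

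- The metric rises with age. Age alone then pushes r in the direction that Section 2.0 predicts, and an age effect can be read as support for the hypothesis.
- The metric falls with age. Age then pushes r the other way and can hide a real link.

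The plain r alone cannot show which case applies. Section 1.0 proposes neuroinflammation as a mechanism of cognitive impairment, so later work would build on what this correlation appears to show.

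**Working it through.** **Inputs from the documents.** Group size is 10, reading Aim 2 as the obese group only (Sections 3.1.1 and 3.3). Eligible ages are 18 to 75 (Section 3.1.1). The plan states no expected correlation, power or alpha, so there is no figure of its own to reproduce.

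**Assumptions.** Age is uniform over 57 years and scaled to unit variance. The metric correlates *m* with age, and the score correlates -*s* with age. The correlation given age, ρ, is 0 or -0.5. A two-sided 5% level serves as a yardstick only. In the results, *m*/*s* gives the two age correlations.

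**Formula.** The population value of plain r is

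r = -*m s* + ρ √((1 - *m*²)(1 - *s*²)).

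- No link, 0.5/0.5: -0.5 × 0.5 = -0.25.
- No link, 0.7/0.7: -0.7 × 0.7 = -0.49.
- True link -0.5, 0.5/0.5: -0.25 - 0.5 × 0.75 = -0.625.
- True link -0.5, -0.5/0.5: +0.25 - 0.5 × 0.75 = -0.125.

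The age-partial r targets ρ in every case. Simulated means at n = 10 sit slightly closer to zero than these values, as expected in small samples.

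**Critical values.** |r| = t/√(df + t²). Plain r has 8 df, giving 0.632. Partial r on age has 7 df, giving 0.666.

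**No true link** (simulated samples of 10). RMSE is taken around the age-adjusted value.

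| Age correlations (*m*/*s*) | Plain r: false positives | Partial r: false positives | RMSE, plain v partial |
|---|---|---|---|
| 0.1/0.3 | 5.1% | about 5% | 0.335 v 0.353 |
| 0.3/0.3 | 5.6% | about 5% | 0.341 v 0.353 |
| 0.3/0.5 | 6.8% | about 5% | – |
| 0.4/0.5 | 8.3% | about 5% | – |
| 0.5/0.5 | 10% (mean r -0.24) | about 5% | 0.394 v 0.354 |
| 0.6/0.6 | 17% (mean r -0.35) | about 5% | – |
| 0.7/0.7 | 31% (mean r -0.48) | about 5% | 0.544 v 0.354 |

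If the enrolled ages span only 30 years, with the same slopes and noise, the last three plain-r rates fall to about 5.5%, 6.4% and 8.7%.

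**True link of -0.5.** Partial r has mean -0.48 and RMSE about 0.286, and reaches the yardstick 29% of the time in each setting.

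| Age correlations (*m*/*s*) | Plain r: mean | Plain r: RMSE | Plain r: reaches yardstick |
|---|---|---|---|
| 0.1/0.3 | -0.48 | 0.267 | 33% |
| 0.3/0.3 | -0.52 | 0.254 | 39% |
| 0.5/0.5 | -0.61 | 0.247 | – |
| 0.7/0.7 | -0.73 | 0.284 | – |
| -0.3/0.5 | -0.25 | 0.401 | 10% |
| -0.5/0.5 | -0.11 | 0.504 | 5% |

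Plain r has the smaller total error when age relations are weak, or when the link and the bias point the same way, although in the second case its mean overstates the link. It does much worse when the metric falls with age.

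**Age-corrected scores with plain r.** If the correction removes the whole age trend, the false-positive rate is 5.0%. The population value is then ρ√(1 - *m*²), because age variation stays in the metric. At *m* = 0.5 this is -0.5 × 0.866 = -0.433. Simulated means are -0.41, -0.38 and -0.34 when both age correlations are 0.5, 0.6 and 0.7. If the correction removes half the trend, the false-positive rates are 6.5%, 8.7% and 13.6%.

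**The case against.** The strongest reply is about weight.

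- **The size is assumed.** No age correlation is documented, and weak or moderate values give rates of 5% to 7%. The documents do not favour the top of the range over the bottom. This stands: the claim is that r can be biased, not that it will be by a given amount.
- **Adjustment is not always better.** With a true link and weak age relations, plain r has smaller RMSE (0.267 v 0.286 at 0.1/0.3) and reaches the yardstick more often (33% v 29%). RMSE is also measured around the age-adjusted value, which makes that value the target. Both points stand. But the proposed mechanism makes the age-adjusted association the more relevant one, and plain r is still reported.
- **Age-corrected scores may already deal with most of it.** With full correction and no link, RMSE is 0.334 against 0.354 for partial r. With a true -0.5 it is 0.297 v 0.286 at 0.5/0.5 and 0.342 v 0.287 at 0.7/0.7. This stands in part: Section 3.2.6 does not commit to such scores, and their benefit depends on how well the correction fits this sample.
- **The background sentence describes one cohort's result**, not a rule for this analysis, and it also names education. True, so it is supporting context only. The main argument is the contrast between Aims 1 and 2.
- **It is a pilot with n = 10.** For an observed r of -0.35 the 95% CI is (-0.80, 0.36) plain and (-0.82, 0.41) adjusted, so the reading is the same. That limits how serious the point is, but it does not make the unadjusted estimate easier to interpret.

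**Conclusion.** The concern holds. As written, Aim 2 cannot separate a metric–cognition link from a shared relation of both with age, although Aim 1 adjusts the same metrics for age. The effect runs from negligible (5.1% false positives at 0.1/0.3) to large (31% at 0.7/0.7, or a true -0.5 reduced to a mean of -0.11 at -0.5/0.5).

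These figures rest on assumed age correlations, uniform ages over the full eligible range and n = 10; a narrower enrolled age range shrinks them considerably. The claim concerns bias only, since neither estimator has the smaller total error everywhere. Adjusting for age removes one confounder and does not make the association causal. The point should be fixed because the remedy is cheap; confidence in its practical size is medium.

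**What to change.** In Section 3.3, make the main Aim 2 estimate the partial correlation of metric and score given age (or the regression of score on metric and age), with a 95% CI. Report plain Pearson r beside it as descriptive, and label Aim 2 exploratory.

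Keep the other Aim 1 covariates for a sensitivity analysis. Age, sex and insulin resistance together leave 10 - 2 - 3 = 5 df and raise critical |r| to 0.754. If gender is entered separately from sex, as the Aim 1 list suggests, 4 df remain.

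In Section 3.2.6, state the score type. If age-corrected scores are used, keep age in the model as well, because plain r on corrected scores is not a full substitute.

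The cost is two sentences in Section 3.3 and one in 3.2.6. Age is already needed for eligibility and Aim 1, so no data are added. Statistically, the change uses one df (critical |r| 0.632 to 0.666), widens the interval slightly, and raises total error a little when age relations are weak or when a real link and the age bias agree in sign.

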4.0. DATA SAFETY MONITORING

These are not clinical trials as defined by NIH. The independent data and safety monitor is [name] [name], M.D. She will monitor the study for unanticipated problems, life-threatening events or deaths.

The Data and Safety Monitoring Plan (DSMP) for this project includes monitoring any adverse events and reporting by [name] and the PI for this protocol. [name] will meet quarterly with the PI and other study personnel to discuss the study. Any serious adverse events or other adverse events are reported to the Washington University's Human Research Protection Office (HRPO) and to the Radioactive Drug Research Committee (RDRC).

Serious adverse events (SAEs) will be reported to HRPO within 7 calendar days using the eIRB Notification System. In the case of an SAE, the study is not resumed until authorized by HRPO. Stopping criteria for an individual participant, in addition to the participant's wish to

Protocol

Version 6: August 25, 2020

stop for any reason, include evidence of harmful side-effects of the research procedures. In the absence of adverse events, summary reports are provided annually to HRPO.

4.1. Human Subjects Education Certification

All key personnel involved in the design or conduct of research involving human subjects will receive the required education on the protection of human research participants prior to the performance of these studies.

4.2. Procedures for Maintaining Confidentiality and Data Security

All staff present will be HIPAA certified and essential to conduct the study. Any potential observers for educational purposes will be allowed only at the discretion of the subject. After consent, we will assure the subjects that no information regarding third parties will be asked or recorded. We will collect information as described in the protocol but if subjects decide that they no longer want to participate, we will not collect any more information. We will assure all subjects that their participation in this study will be held in the strictest of confidence.

Paper data will be stored in a locked file drawer in the East Building, which is a secured building. All data will be de-identified utilizing a code number. The material obtained from the research participants is specifically for research purposes and will only be shared among the study team members. Electronic data is stored in a private, firewall protected, password protected manner on a drive specified for research data. All research data will only be available to members of the research team.

Saliva obtained for genotyping purposes will not be saved. Blood obtained for OGTT and peripheral immune measures will not be saved after analyses are complete.

The following privacy protections will be enacted for all e-mail communications involving PHI:

- 1) a test e-mail will be sent to the participant to verify their identity (confirm correct recipient) and that this e-mail will be sent in a secure manner (i.e., [secure] in subject line);
- 2) the body of the e-mail will instruct the participant to send all information as a response to this thread and to not remove the “[secure]” from the subject line;
- 3) We will document in our research records the participant’s agreement to provide information over e-mail.

4.3. Risks and Benefits

We see no psychosocial, social or legal risks beyond those of participating in non-therapeutic research *per se*. The physical risks are those associated with intravenous lines (bruising and very low risk of infection), discomfort from lying flat (including lying flat for 1.5 hour for the MRI), and possible risk of claustrophobia. All research carries some risk of loss of confidentiality.

4.3.1. Likely Risks:

There are no known physical risks to subjects receiving MRI scans who meet our inclusion and exclusion criteria.

4.3.2. Less Likely Risks:

Protocol

Version 6: August 25, 2020

Risks of i.v. placement, including pain, bleeding, bruising, and infection.

Participants may develop mild muscle aches and pains due to immobility and exposure to the acoustic noise of the MRI scanner. The development of muscle aches and pains is minimized by providing appropriate cushions at pressure points and beneath the knees as desired by the subject. Ear phones or earplugs will be used to dampen the sound of the MRI procedure. Participants may feel anxious when in the MR scanner. However, participants will be able to communicate with us throughout the scan and can tell us whenever they want the scan to be stopped or interrupted. Subjects may experience claustrophobia when placed in a MRI scanner. This can occur without a prior history of claustrophobia.

The risk of having IVs placed and blood samples taken include soreness or slight bruising at the site of the blood draw. Further risks of the OGTT are nausea and lightheadedness.

The risks of performing cognitive testing include frustration when tasks are difficult and fatigue.

4.3.3. Rare Risks:

Loss of confidentiality.

There is a potential risk of heart rhythm disturbances in individuals who have previous rhythm abnormalities or in patients with certain types of heart pacemakers. Because individuals with heart rhythm disturbances or pacemakers might be harmed by being in the MRI scanner, they should not participate in the study. There is a substantial risk to individuals who have metallic objects inside their bodies because the MRI scanner uses a high strength magnet. This risk involves the metallic objects being pulled by the magnetic field, which would cause physical harm. The following items may interfere with the MRI scans and some can potentially be hazardous: Cardiac pacemaker, aneurysm clip(s), implanted insulin/drug pump, neurostimulator (TENS unit), biostimulator/bone growth stimulator, hearing aid/cochlear implant, Gianturco coil (embolus coil), vascular clip(s), surgical clip or staple(s), heart valve prosthesis, Greenfield vena cava filter, middle ear implant, penile prosthesis, shrapnel or bullet, wire sutures, tattooed eye liner, any type of dental item held in place by a magnet, any other implanted item not mentioned, diaphragm/IUD, intraventricular shunt, wire mesh, artificial limb or joint, any orthopedic item (i.e., pins, rods, screws, nails, clips, plates, wire, etc.), dentures, dental braces, any type of removable dental items, or pregnancy. Participants complete an MR screening form to screen for these items and will not be consented if they meet any of the above rare risk factors. Thus, if participants have any of the above, they will be excluded from the study.

4.3.4. Benefits:

Direct benefits to the participating subjects are not anticipated. To the extent of societal benefit, it leads to a better understanding of the occurrence of neuroinflammation in obesity and whether it contributes to cognitive impairment in obesity. Given these potential benefits and our efforts to minimize risks, the risks of this study are reasonable in relation to the benefits.

Protocol

Version 6: August 25, 2020

